# 4.0 RESEARCH METHODOLOGY

#### 4.1 Study design

Prospective, randomized controlled clinical trial

#### 4.2 Place of study

Obstetric ward and maternity operation theatre of Department of Obstetrics and Gynaecology, Universiti Kebangsaan Malaysia Medical Centre (UKMMC).

#### 4.3 Study Population

All women undergoing elective caesarean section, without any history of previous abdominal surgery; who planned for further pregnancy and consented to participate in this study.

#### 4.4 Duration of study

6 months duration; from April 2017 to October 2017

#### 4.5 Inclusion Criteria

Pregnant women without any history of previous abdominal surgery

Plan for elective caesarean section for this current pregnancy section

Transverse suprapubic scar

#### 4.6 Exclusion Criteria

Patient who are allergic to protescal Patient with previous abdominal surgery Patient with surgery complication

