#### 4.7 Randomization

The randomization sequence, either to Protescal group or control group, was generated by using a computer randomization program; in the maternity operation theatre or antenatal clinic .

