#### 4.8 Data Collection And Statistical Analysis

SPSS (Statistical Package of Social Science) version 20.0 will be employed proportional data will be compared with chi square. The Fisher exact test will be chosen if the expected size of any cell of the contingency table is less than 5. Continuous data will be compared using the Wilcoxon rank-sum test. Multiple logistic regressions will be use to model the relationship between group assignment, controlling for possible confounders. P<0.05 will be considered significant.

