#### 4.9 Sample Size Calculation

- The sample size was calculated based on computerized generated formula, Cohen's (1988) formula.
- Effect size calculator for T Test
- For the independent samples T-test, cohen's d id determined by calculating the mean difference between two groups, and then dividing the result by pooled standard deviation

cohen's d = M2 - M1/SD pooled

SD pooled =  $\sqrt{((SD1^2 + SD2^2)/2)}$ 

• Using effect size f = 0.60, alpha = 0.05 and power = 0.80, the appropriate number of participants was calculated as 45 in each group.

D											
Power	0.10	0.20	0.30	0.40	0.50	0.60	0.70	0.80	1.0	1.20	1.40
0.25	332	84	38	22	14	10	8	6	5	4	3
0.50	769	193	86	49	32	22	17	13	9	7	5
0.60	981	246	110	62	40	28	21	16	11	8	6
2/3	1144	287	128	73	47	33	24	19	12	9	7
0.70	1235	310	138	78	50	35	26	20	13	10	7
0.75	1389	348	155	88	57	40	29	23	15	11	8
0.80	1571	393	175	99	64	45	33	26	17	12	9
0.85	1797	450	201	113	73	51	38	29	19	14	10
0.90	2102	526	234	132	85	59	44	34	22	16	12
0.95	2600	651	290	163	105	73	54	42	37	19	14
0.99	3675	920	409	231	148	103	76	58	38	27	20

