**Cohen's Sample Size Table** 

# 4.10 Study Flow Chart

 $\downarrow$ 

Protescal applied at uterine suture site and in subcutaneous tissue layer prior to skin closure

No protescal applied at uterine suture site and in subcutaneous tissue layer prior to skin closure

After delivering the baby through caesarean section, uterine muscle is closed in 2 layers with braided absorbable suture, polyglactin 910 (vicryl no 1).

After haemostasis secure, 4 ml Protescal gel apply at the uterine suture site.

Peritoneal layer close using braided absorbable suture, polyglactin 910 (vicryl no 1).

Rectus sheath suture using braided absorbable suture, polyglactin 910 (vicryl no 1).

Subcutaneous tissue close interruptedly using braided absorbable suture, polyglactin 910 (vicryl no 1).

1 ml Protescal gel apply in subcutaneous tissue prior to skin closure.

Skin close with subcuticular method using braided absorbable suture, polyglactin 910 (vicryl 3-0).

Wound healing assess on 10th day post caesarean section using REEDA scale, which had criteria including redness, edema, ecchymosis, discharge and approximation.

On 3rd month, the degree of scarring assess using the Vancouver scar scale including pigmentation, height, pliability and vascularity.

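### The exclusion for surgery complications has no time window, can remove women after allocation, and is not offset by any as-randomised analysis rule

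*Combined protocol and SAP*

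**What the plan says.** Section 4.6 lists three exclusions: allergy to the gel, previous abdominal surgery, and "Patient with surgery complication". The third has no definition, time window or named judge.

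The surrounding text bears on its meaning:

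- Section 4.3 describes the population as "All women undergoing elective caesarean section, without any history of previous abdominal surgery", together with a plan for further pregnancy and consent. It says nothing about complications.
- Section 4.5 requires a "Plan for elective caesarean section for this current pregnancy section". The operation has not happened when a woman enters.
- Section 4.7 says the sequence was computer-generated "in the maternity operation theatre or antenatal clinic". It does not give the moment of allocation.
- Section 4.8 names tests (for example, "Continuous data will be compared using the Wilcoxon rank-sum test"), a logistic regression and a significance level. It does not say which women are analysed.
- Section 4.9 states that "the appropriate number of participants was calculated as 45 in each group". It does not say whether this means women randomised or women analysed, or whether excluded women are replaced.
- Section 4.10 applies the gel during surgery, first at the uterine suture and then under the skin. It scores the wound on day 10 with REEDA, "which had criteria including redness, edema, ecchymosis, discharge and approximation". At month 3, "the degree of scarring assess using the Vancouver scar scale including pigmentation, height, pliability and vascularity".

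**The concern.** Read as a complication of the trial caesarean, the criterion selects women on something that can happen after allocation and after the gel has been placed in the wound being assessed. If the gel changes the complication rate, or if complications are judged differently in the two arms, the women left for analysis are no longer the randomised groups. The estimate of the gel's overall effect is then biased. If the gel raised complications, removal would hide that harm. If it lowered them, removal would hide that benefit.

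The link to the outcome is direct at day 10, because edema, ecchymosis, discharge and poor approximation are signs of a complicated wound as well as scored items. It is weaker for the month-3 Vancouver items. No surviving text describes blinding of whoever judges a complication, so unequal removal is not ruled out. Because the term is undefined, two teams following the same protocol could also analyse different women.

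**Working it through.** **Step 1: what the criterion refers to.** Previous abdominal surgery has its own exclusion, so a complication of earlier abdominal surgery would add nothing. The caesarean is only planned at entry (4.5), so its complications cannot be known at screening. The trial operation is the natural referent.

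**Step 2: when it bites.** The gel goes in before the skin is closed (4.10). Any postoperative complication therefore follows allocation, wherever allocation takes place. An intraoperative complication could precede allocation only if allocation is made late, in theatre.

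**Step 3: whether the analysis offsets it.** Section 4.8 has no as-randomised rule and no analysis set. Adjusting for confounders does not restore a randomised comparison.

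**Step 4: the plan's own figure.** Inputs from 4.9: effect size 0.60, alpha 0.05, power 0.80. Sidedness is not stated. The two-sided two-sample t-test (noncentral t) gives 44.59, rounded up to 45 per group, which matches. Power at 45 is 0.804.

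**Step 5: bias illustrations.** All rates, excess scores and removal fractions are assumptions. There are 45 randomised per arm, SD is 1 in uncomplicated women, and complicated wounds score D worse (D = 1 or 1.5 SD). With complication rates p1 and p2 and equal uncomplicated women, the overall difference is D × (p1 − p2). If a share a of complications with rate p is removed, the arm mean shifts by D × p(1 − a) / (1 − pa). Rejection rates come from 60,000 simulated trials per scenario, using a two-sided t-test.

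| Scenario | True overall difference | Difference after removal | Rejection after removal |
|---|---|---|---|
| (a) Inert gel, 10% v 10%, D = 1.5, all removed | 0 | 0 | 0.049 |
| (b) 10% v 5%, D = 1, all removed | 1 × 0.05 = 0.05 | 0 | 0.049 |
| (b) 15% v 5%, D = 1.5, all removed | 1.5 × 0.10 = 0.15 | 0 | 0.050 |
| (c) Inert gel, 10% v 10%, D = 1, all removed in one arm, half in the other | 0 | 1 × 0.05/0.95 = 0.053 | 0.056 |
| (c) As above, D = 1.5 | 0 | 1.5 × 0.05/0.95 = 0.079 | 0.062 |

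Scenario (a) has no bias. In (b) a real difference disappears, which is not a false positive. In (c) a small false difference appears.

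**Step 6: power.** This assumes that 45 is the number randomised and that women are not replaced. Losing 5%, 10% or 20% leaves 42.75, 40.5 or 36 per group, and t-test power at 0.60 falls to 0.783, 0.760 or 0.709. Keeping the women does not recover this. With 10% complications the SD becomes √(1 + 0.10 × 0.90 × D²), which is 1.044 for D = 1 and 1.097 for D = 1.5. Power with all 45 kept is then 0.77 or 0.73, against 0.76 when they are removed.

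**The case against.** The best counter-argument is that the text does not force the post-allocation reading. The eligibility lists already repeat one another, so non-overlap between items is weak evidence of meaning. Section 4.3 also omits the allergy exclusion, so its silence says nothing about timing. Section 4.5 asks for a transverse suprapubic scar in women with no earlier abdominal surgery, which suggests that eligibility may be completed during the operation. Section 4.7 may describe only where the sequence was generated, and the top of the flow chart, which may have shown allocation, is lost. If allocation were made in theatre once haemostasis is secure, earlier intraoperative complications would be ordinary pre-allocation exclusions.

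These points stand as reasons for caution, and they are why the criterion is said only to be able to remove women after allocation. They do not reach postoperative complications, which follow allocation under any reading of 4.7.

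The second objection is size. On the assumed inputs in (b), keeping every woman would give rejection of only about 0.056 (10% v 5%, D = 1) or 0.096 (15% v 5%, D = 1.5), so the trial's significance test would rarely change. Scenario (c) needs complications to be judged differently by arm, which nothing in the documents indicates. The overlap is mainly with day-10 REEDA, whereas the month-3 scale is closer to the hypertrophic-scar objective. All of this is fair. It limits the likely size of the problem but does not make the remaining women a randomised comparison, nor does it show a harm that has been excluded from view.

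**Conclusion.** The concern holds, with moderate confidence, and should be fixed. On its natural reading the exclusion can remove women after allocation for an event related to the wound outcome, and nothing in the surviving analysis section counters this.

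The size and direction of any bias cannot be obtained from the documents. Under the assumed rates and excess scores it is modest: 0.05 to 0.15 SD of real effect concealed, or 0.05 to 0.08 SD of spurious effect, beside a planned 0.60. There is no bias if the gel is inert and removal is equal, or if the exclusion operates only before allocation. The argument rests on bias and on hidden harm or benefit, not on power.

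**What to change.** - **Section 4.6:** limit the exclusion to complications evident before allocation, or state whatever other meaning was intended.
- **Section 4.8:** state that every randomised woman is followed and analysed in her allocated group whatever complication follows, and that complications are tabulated by arm. Say also how women without a day-10 or month-3 score are handled, since the as-randomised rule alone does not settle that.
- **If women have already been excluded under this criterion:** report their number by arm and by timing relative to allocation, and include them in the analysis where outcomes exist.
- **Optional:** open the allocation in theatre just before the arms first differ. This reduces the number of intraoperative events that fall after allocation.

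The cost is a few sentences and one table. Complicated wounds stay in the analysis and add variability: with an assumed 10% scoring 1 to 1.5 SD worse, t-test power at 45 per group is 0.77 to 0.73 instead of 0.80.

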#### 4.7 Randomization

The randomization sequence, either to Protescal group or control group, was generated by using a computer randomization program; in the maternity operation theatre or antenatal clinic .

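### Section 4.7 has no step that conceals the next allocation or fixes consent and eligibility before the arm is known, so women could be entered or removed with the arm known

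*Combined protocol and SAP*

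**What the plan says.** Section 4.1 labels the study "Prospective, randomized controlled clinical trial" and mentions no masking. Section 4.7 is a single sentence: "The randomization sequence, either to Protescal group or control group, was generated by using a computer randomization program", followed after a semicolon by "in the maternity operation theatre or antenatal clinic". The type of sequence, block scheme, custodian and method of release are not given.

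Section 4.2 gives the place of study as "Obstetric ward and maternity operation theatre of Department of Obstetrics and Gynaecology". The theatre is therefore both a study site and one of the two locations in 4.7. The antenatal clinic appears only in 4.7.

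In the flow chart (4.10) the treated arm reads "Protescal applied at uterine suture site and in subcutaneous tissue layer prior to skin closure". The control arm has the same line with a leading negative: no gel at either site, and no sham or placebo gel. The gel goes first to the uterine suture line and later to the subcutaneous layer.

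Section 4.6 lists "Patient with surgery complication" as an exclusion and does not say when it is applied. Section 4.3 mentions consent ("who planned for further pregnancy and consented to participate in this study") but does not place it before or after allocation. Section 4.8 lists tests and a regression model and does not define which randomized women are analysed.

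**The concern.** A computer-generated sequence protects against selection only if nobody deciding on entry can foresee the next arm, and if entry cannot be undone once the arm is seen. The plan secures neither.

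Before allocation, a clinician who knew the next arm could offer, delay or withhold entry for a particular woman. After allocation, a woman could be dropped under the surgical-complication exclusion by a surgeon who already knows whether gel is being used. Judging what counts as a complication leaves some discretion, and no rule keeps such a woman in the analysis.

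Both routes can make the arms differ in scar prognosis for reasons other than the gel. The introduction itself says that the final scar depends partly on patient and wound factors. Masked scoring of the scar would not help, because the damage is done before any scar is scored. Regression on measured confounders repairs it only in part.

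**Working it through.** **1. The passages side by side.**

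| Question | What the plan gives |
|---|---|
| Who generates and holds the sequence? | Not stated (4.7) |
| What hides the next assignment? | Nothing stated: no envelopes, no central, telephone, web or pharmacy release |
| Are consent and eligibility fixed first? | Not stated (4.3, 4.5 to 4.7) |
| Does the surgeon know the arm once assigned? | Yes, because controls get no gel (4.10) |
| Can a woman be excluded after that? | Yes: the surgical-complication exclusion (4.6) has no time limit |
| Is she then kept in the analysis? | Not stated (4.8) |

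The semicolon in 4.7 allows two readings. If the locations are where the sequence is produced, it is produced at or near the point of care. If they are where women are allocated, nothing is said about how an assignment reaches the clinician. The safeguard is absent under both.

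**2. The plan's own figure.** Section 4.9 states "Using effect size f = 0.60, alpha = 0.05 and power = 0.80" and 45 per group. Although labelled f, the 0.60 behaves as Cohen's d. The normal approximation gives n = 2 × (1.960 + 0.842)² / 0.60² = 43.6, so 44 per group. The exact two-sided t-test needs 44.6, so 45, with power 0.804 at 45. The figure reproduces, and adding concealment does not change it.

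**3. A hypothetical scale.** The documents contain no figure on steering, so the next two inputs are assumptions:
- a prognostic factor worth 0.5 SD on the scar score;
- a difference of 20 to 40 percentage points between arms in how often it occurs, which is 9 to 18 of 45 women (0.20 × 45 and 0.40 × 45).

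Bias = 0.5 SD × 0.20 = 0.10 SD, up to 0.5 SD × 0.40 = 0.20 SD. As a share of the planned 0.60 SD this is 0.10/0.60 = 17% to 0.20/0.60 = 33%.

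The standard error of the difference, in SD units, is √(2/45) = 0.211. With no true effect the test statistic is therefore centred at 0.10/0.211 = 0.47 or 0.20/0.211 = 0.95 instead of 0. Two-sided rejection rates at a nominal 5%:

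| Bias | t-test | Normal approximation |
|---|---|---|
| 0.10 SD | 7.6% | 7.6% |
| 0.20 SD | 15.5% | 15.8% |

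**The case against.** The strongest reply is that silence is not a defect. The plan nowhere says that clinicians see a list. A program run on demand, which issues an arm only after irrevocable entry, has nothing to read ahead and would be adequate. The visible flow chart also begins part-way down, so an enrolment or randomization box may have been lost in text extraction. Both points are fair. They bar the claim that the next arm was in fact known. They do not supply the safeguard, which belongs in 4.7 and is not there.

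Four stronger readings are tempting, and the documents do not support them:
- **That women are recruited in the antenatal clinic.** This is a natural inference for elective surgery, but no section says so, and 4.2 does not list the clinic.
- **That a woman could be allocated twice, or that two lists exist.** Section 4.7 joins the two places with a plain alternative; nothing points to a repeat allocation.
- **That clinicians favour the gel and would steer women towards it.** No motive is documented, and no direction of bias follows.
- **That the false-positive rate in this trial is 8% to 16%.** Both steering inputs are assumed, and a net shift of 18 women in 45 is heavy. Women with earlier abdominal surgery are excluded, so there is no old abdominal scar to judge by, though other cues could exist. The calculation uses a t-test, as 4.9 does, while 4.8 plans a Wilcoxon rank-sum test. The planned regression could remove part of any measured imbalance, but it names no covariates and cannot reach unmeasured prognosis.

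**Conclusion.** The point holds as a gap in design protection. As written, the plan permits women to be entered, or removed under the surgical-complication exclusion, with the arm known. It does not show that this happened or was intended.

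The conclusion rests on the wording of 4.6, 4.7 and 4.10 and not on the numerical illustration, which gives only a sense of scale: 0.10 to 0.20 SD of bias and a false-positive rate of about 8% to 16% under assumed steering, with 45 per group and no true effect. The plan should be changed, because what happens at entry cannot be fully repaired in analysis and the remedy is cheap. If adequate concealment already exists in practice, writing it into 4.7 settles the matter.

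**What to change.** Replace 4.7 with a procedure that contains these elements:

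1. One computer-generated 1:1 list in randomly varying permuted blocks, with a few spare allocations beyond 90 (2 × 45), prepared and held by an existing staff member who neither recruits nor operates.
2. Allocations in sequentially numbered, opaque, sealed envelopes.
3. The next envelope opened only after consent, study number and confirmed eligibility are logged, and as late as practical before the first gel application. The surgical-complication exclusion is then applied before the arm is known, as far as possible.
4. The time of opening logged.
5. Every woman whose envelope is opened reported, and analysed in her allocated arm. Say the same in 4.8.

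State in 4.6 at what point the surgical-complication exclusion stops applying, so that it agrees with items 3 and 5.

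**Cost:** about half a page of protocol, somewhat more than 90 envelopes, a log sheet, and the time to prepare and keep them. No extra staff, no change to the sample size and no change to treatment.

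### Section 4.7 can be read as allowing allocation in the antenatal clinic, before it is known that a woman will reach the operation at which the gel is given; allocation should be confined to theatre

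*Combined protocol and SAP*

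**What the plan says.** - **Place of randomisation.** Section 4.7 is a single sentence. The sequence "was generated by using a computer randomization program", and the place given is "in the maternity operation theatre or antenatal clinic". It gives no time relative to surgery and no re-check of eligibility.
- **Entry criterion.** Section 4.5 asks for "Plan for elective caesarean section for this current pregnancy section", which a woman can meet at a clinic visit. It also lists "Transverse suprapubic scar". Because earlier abdominal surgery is excluded, this can only be the scar of the index operation.
- **Population.** Section 4.3 describes "All women undergoing elective caesarean section, without any history of previous abdominal surgery".
- **Time of treatment.** In section 4.10 the arms differ only within the operation: "Protescal applied at uterine suture site and in subcutaneous tissue layer prior to skin closure" against no gel at either site. The first application comes once the uterus is closed: "After haemostasis secure, 4 ml Protescal gel apply at the uterine suture site".
- **Handling of affected women.** Section 4.8 defines no analysis population. Section 4.9 sets 45 women per group with no allowance for women who are randomised and then untreated or not assessable.

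**The concern.** Nothing that differs between the arms happens before the uterus is closed. Allocation at a clinic visit leaves an interval in which the plan for an elective transverse caesarean can change: labour may start first, the delivery may be vaginal, or a different incision may be used. Such a woman met the planned-surgery criterion when she was allocated, but she may not have the operation or scar that the trial studies.

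The protocol has no rule for her. If she is kept and scored, a gel-arm woman who received no gel pulls the two arms together. If she is removed, the groups compared are no longer the groups randomised, and bias becomes possible if removal differs by arm. Allocation in theatre, which 4.7 already names, avoids both outcomes for women who never reach the eligible operation.

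**Working it through.** **Inputs from section 4.9.** Effect size 0.60 (labelled f, but used as Cohen's d), alpha 0.05, power 0.80, 45 per group. Sidedness is not stated; two-sided is used because it reproduces the stated number.

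**Assumed input.** The share q of randomised women who do not reach the planned operation. The documents give no figure, so 5%, 10% and 15% are shown.

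**Formula.** Two-sample t-test power from the noncentral t distribution with 2n − 2 degrees of freedom and noncentrality d × √(n/2), where n is the number per group.

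**Step 1: the plan's own figure.** Solving for power 0.80 at d = 0.60 gives 44.6, rounded up to 45 per group, as stated. At n = 45 the noncentrality is 0.60 × √22.5 = 2.846 and power is 0.804. There is almost no reserve.

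**Step 2: affected women kept (worst case).** Suppose every affected gel-arm woman goes without gel, gains no benefit and is still scored. The expected effect becomes d × (1 − q), with n = 45.

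| q | Effect | Power |
|---|---|---|
| 5% | 0.60 × 0.95 = 0.57 | 0.762 |
| 10% | 0.60 × 0.90 = 0.54 | 0.717 |
| 15% | 0.60 × 0.85 = 0.51 | 0.667 |

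**Step 3: affected women dropped equally from both arms.** The effect stays at 0.60 and n becomes 45 × (1 − q), rounded to whole women.

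| q | n per group | Power |
|---|---|---|
| 5% | 42.75, taken as 43 | 0.785 |
| 10% | 40.5, taken as 40 | 0.755 |
| 15% | 38.25, taken as 38 | 0.733 |

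This counts only lost precision. Bias from unequal dropping would be additional and cannot be sized from the documents.

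**Step 4: only some women allocated in clinic.** Here q is a share of all randomised women. If half were allocated in clinic and 10% of those were affected, q = 0.5 × 10% = 5%. Power in the kept case is then 0.762, not 0.717.

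**The case against.** **The place may belong to the sequence.** Grammatically, the location in 4.7 attaches to generating the sequence, not to assigning a woman. Section 4.2 lists the obstetric ward and the maternity theatre as study sites, not the antenatal clinic. The part of the flow chart above the two arm boxes was not readable in the text used here and may show when allocation occurs. This stands as a reason for caution: a reader might infer that clinic allocation is the settled design, and the documents do not establish that. But no other readable text says where or when a woman is assigned, so the ordinary reading of 4.7 allows it. If the sponsor meant otherwise, the sentence still needs correcting.

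**Sections 4.3 and 4.5 are not opposed.** A reader might infer that they give contradictory answers on who is in the trial. They do not: undergoing an elective caesarean can naturally mean being scheduled for one, and the same sentence in 4.3 speaks of consent, which comes before an elective operation. The wording is loose and needs aligning.

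**The size is assumed, and the kept case is a worst case.** This stands. A woman who delivers vaginally has no caesarean scar to score, so she cannot dilute that outcome. A woman whose caesarean becomes an emergency might still receive gel. The documents also do not say who knows the allocation or when, so removal with knowledge of the arm is a possibility, not a finding.

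**Theatre allocation is not a complete cure.** This also stands. The exclusion in 4.6, "Patient with surgery complication", can still apply after a woman has been allocated in theatre.

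**Conclusion.** The point holds in a limited form. As worded, 4.7 leaves room for allocation before a woman is known to reach the operation at which the gel is given and the incision criterion can be confirmed, and nothing in the plan says what happens to her if she does not.

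The size cannot be derived from the documents. With an assumed 5% to 15% of all randomised women affected, power falls from 0.80 to 0.76–0.67 in the worst kept case, or to 0.79–0.73 if women are dropped equally. Both ranges shrink if only some women are allocated in clinic. The case for the change does not depend on the rate: treatment starts only in theatre, and 4.7 already allows allocation there.

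It would go too far to say that theatre allocation guarantees an intact randomised comparison. It deals with women who miss the eligible operation, not with exclusions for complications that arise after allocation.

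**What to change.** 1. In 4.7, delete the reference to the antenatal clinic and state separately how the sequence is generated and when and where each woman is assigned.
2. Take consent beforehand. Allocate in theatre at the elective operation, after eligibility is confirmed (including that the incision is transverse) and before the first point at which gel would be applied.
3. Align the wording of 4.5 with 4.3, so that both refer to women undergoing the elective operation.
4. Count women who consent but do not reach this point as screened, not randomised.

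The cost is protocol wording, one allocation step carried out in theatre, and a few consented women who are never randomised. Exclusions for complications arising after allocation need their own rule.
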